3.6.5.2. SECONDARY EFFICACY ENDPOINTS

All secondary efficacy endpoints will be summarized by treatment group, using the observed data in the mITT population. For continuous secondary efficacy endpoints, summary statistics include mean, standard deviation, median, minimum and maximum, while for categorical secondary efficacy endpoints frequencies and proportions are provided.

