Secondary endpoints will include the composite systemic lupus erythematosus responder index (SRI), the individual components (SLEDAI-2K, BILAG-2004 [normal improvement, enhanced improvement, and individual item improvement], and physician's global assessment [PGA]), patient's global assessment, 28 joint count, cutaneous lupus erythematosus disease area and severity index (CLASI), incidence of flare rate and potential for steroid reduction. Health-related quality of life (SF-36) will be used as supportive evidence of efficacy. In addition, endpoints, including BICLA responses, SRI responses and SLEDAI-2K, and BILAG-2004, will be documented over time, including earlier time points allowing assessment of time of onset of the effect.

Safety and tolerability assessments will include evaluation of (serious) AEs (including injection site and hypersensitivity reactions), laboratory assessment (including but not limited to acute phase proteins, neutrophils, platelets, liver enzymes and lipids), urinalysis, vital signs, electrocardiogram (ECG), and physical examination.

Additional planned assessments include the determination of ALX-0061 levels in serum and PD biomarkers (including sIL-6R) in blood. To assess immunogenicity, the presence of ADA will be measured in serum using a conventional ADA assay, with potentially further characterization by modified ADA (mADA) and neutralizing antibody (nAb) assay.

Study Treatment Allocation and Eligibility Process

At the Screening Visit, informed consent will be obtained from all subjects who are deemed potentially eligible for the study, according to the protocol-specified inclusion and exclusion criteria, for enrollment in the study. All data obtained at screening will also be centrally assessed in an eligibility evaluation, the sites will be informed whether a subject can be randomized.

At randomization, subjects will be randomized to receive either ALX-0061 or placebo, as described below (also see section [3.4.1.2](#) for additional information on randomization).

Eligible subjects will be randomized to 1 of 5 treatment groups in a 1:1:1:1:1 ratio. Subjects and investigational staff will be blinded for treatment and dose. Subjects will be followed for efficacy through Week 48, and for safety through Week 58.

Treatment Arms

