3.2.3.2. DISCONTINUATION OF STUDY DRUG

Subjects who have to discontinue study drug but are not withdrawing consent for post-treatment follow-up should return for the Early Termination Visit, planned within 3 weeks after the last study drug administration, as well as for the Follow-up Visit planned 12 weeks after the last study drug administration, according to section [3.4.1.3](#).

Study drug administration must be discontinued in case of:

- Withdrawal of consent.
- Serious hypersensitivity reaction.
- Abnormalities in laboratory test results:
 - ALT and/or AST elevations:
 - $> 3 - \leq 5 \times \text{ULN}$, confirmed by repeat testing on 2 consecutive visits
 - $> 5 \times \text{ULN}$ (CTCAE \geq grade 3)
 - absolute neutrophil count $< 1 \times 10^9/\text{L}$ (CTCAE \geq grade 3)
 - platelet count $< 50 \times 10^3/\mu\text{L}$ (CTCAE \geq grade 3)
- Diagnosis or suspicion of a serious infection (requiring parenteral antibiotics and/or hospitalization) if interruption of study drug is needed for more than one dose or if deemed necessary by the Investigator.
- Diagnosis of TB.
- Malignancy.
- Pregnancy or pregnancy planned within study period.
- Initiation of prohibited medication, as discussed with Sponsor/Medical Monitor.
- In case of interruption of study drug administration for 2 consecutive doses.
- The randomization code is broken prematurely by the Investigator or his/her staff.

- Demyelinating disease.
- CHF class III or IV as defined by the New York Heart Association, unstable angina pectoris, myocardial infarction, cerebrovascular accident, thromboembolic event.
- If the Investigator or the Sponsor's Medical Monitor deems it is in the subject's best interest, e.g., in case of renal or CNS flare.

Discontinuation of study drug must be considered for subjects who develop a severe study drug injection-site reaction or a severe hypersensitivity reaction.

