In case of worsening of disease or a flare, the Investigator will decide on the need for increase of dose of oral corticosteroids, use of i.v. or i.m. corticosteroids, start or increase of the dose of anti-malarial or immunosuppressant, according to his/her local clinical practice. The Investigator will also assess if study drug administration can be continued or not, except in case of initiation of forbidden treatment e.g., cyclophosphamide or another biologic, when study drug administration will be discontinued. Subjects needing such change to standard of care therapy for SLE will be considered as treatment failures and imputed as non-responders in the analysis of the primary endpoint. This does not apply to the transient increase in oral corticosteroid dose that is allowed within the protocol until the Week 4 visit (i.e., Week 4 \pm 5 days).

A description of assessments to be performed for subjects who discontinue from the study or study drug is provided in section 3.4.1.3 (also see Early Termination Visit in the [Schedule of Assessments](#)).

For all subjects, every effort should be made to contact the Medical Monitor prior to discontinuing study drug administration, where medically feasible. If there is a medical reason for discontinuation, the subject will remain under the supervision of the Investigator until satisfactory health has returned unless the subject withdraws his/her consent and is no longer willing to come to the visits. Subjects who discontinue will not be replaced.

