3.4.1.3. END OF TREATMENT VISIT AND FOLLOW-UP

Subjects who have received all study medication through Week 46 should return for the assessment visit at Week 48, and for the Follow-Up Visit at Week 58 (12 weeks after the last study drug administration at Week 46).

Discontinuation of Study Drug Administration

Subjects who have to discontinue study drug but are not withdrawing consent for post-treatment follow-up, should return for an early termination visit within 3 weeks after the last study drug administration. Subjects should also return for a Follow-up Visit 12 weeks after last study drug administration to undergo the assessments as specified in the [Schedule of Assessments](#).

Termination of Study Participation

Subjects who terminate study participation for reasons of lost to follow-up, informed consent withdrawal, or death should not return for the Early Termination Visit or for the Follow-up Visit.

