3.4.3.6. BILAG-BASED COMPOSITE LUPUS ASSESSMENT (BICLA)

The composite BICLA response comprises criteria of 3 different validated indices (SLEDAI, BILAG, and PGA) and is defined as follows:

- BILAG-2004 improvement: all A scores at baseline improved to B/C/D, and all B scores improved to C or D.
- no worsening in disease activity: no new BILAG-2004 A scores and ≤ 1 new B score.
- no worsening of total (m)SLEDAI-2K score from baseline.

- no significant deterioration (< 10% worsening) in PGA.
- no treatment failure (i.e., new or increased immunosuppressives or anti-malarials; or non-protocol allowed increased oral or parenteral corticosteroids; or premature discontinuation from study treatment).

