3.4.3.7. SYSTEMIC LUPUS ERYTHEMATOSUS RESPONDER INDEX (SRI)

The composite index SRI enables quantification of decrease and increase in disease activity in a broad spectrum of manifestations thereby offering a comprehensive assessment of SLE disease status [41].

SRI combines advantages from three validated measurement tools:

- SLEDAI covers global disease improvement,
- BILAG covers organ specific disease worsening or improvement and
- PGA is used as a validity and safety net for items that were not addressed by the other two indices.

The composite SRI criteria for response are:

- SLEDAI-2K: ≥ 4 point reduction.
- BILAG: no new A domain score and no more than 1 new B domain score.
- PGA: no worsening (<10% increase).

When all three criteria are met, the subject is a responder according to the SRI at that time point, i.e., a clinically meaningful improvement of disease is detected.

In addition the modified SRI (mSRI) will be assessed, i.e., using the modified (excluding the low component item) version of the SLEDAI-2K as a criterion.

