- Proportion of treatment failures (defined as non-protocol allowed increase in steroid dose, start i.v. or i.m. steroids, start or increase of immunosuppressant) at Week 24 and at Week 48 will be summarized by treatment group.
- Reduction in flare rate at Week 24 and at Week 48.
 - Severe flare defined as a new A score in any system of the BILAG-2004 index; moderate flare defined as a new B score following a C, D or E score.
 - SFI.
- Percent change from baseline in daily dose of steroids at Week 24 and 48 will be summarized by treatment group.
- Percent subjects whose prednisone equivalent dose was >7.5 mg/day at baseline and reduced to ≤ 7.5 mg/day during Weeks 40–48 without experiencing a flare will be summarized by treatment group.
- Percent subjects who are able to discontinue prednisone by Week 48 without experiencing a flare will be summarized by treatment group.
- Changes from baseline in the physical and mental component scores of SF-36 at Week 24 and at Week 48 will be summarized by treatment group.
- 28 Joints count over time and change from baseline in 28 joint count over time will be summarized by treatment group.
- CLASI over time and change from baseline evaluation at Week 12, 24 and Week 48 will be summarized by treatment group.
- PK parameters.
- PD markers, including total sIL-6R, CRP, fibrinogen, anti-dsDNA, C3, C4, CH50.

Descriptive subgroup analyses may be performed to evaluate consistency of the primary endpoint over covariates including demographics (including weight and region), baseline disease, and prior and concomitant medications. Details will be provided in the SAP.

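### (m)SRI has no treatment-failure criterion and is summarised on observed data, so a subject who fails mBICLA through rescue can be an mSRI responder at the same visit

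*Protocol*

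**What the plan says.** - **Analysis rule.** Section 3.6.5.2, repeated in the synopsis: "All secondary efficacy endpoints will be summarized by treatment group, using the observed data in the mITT population".
- **SRI.** Section 3.4.3.7 sets one criterion each on SLEDAI-2K, BILAG and PGA, then: "When all three criteria are met, the subject is a responder according to the SRI at that time point". mSRI changes only the SLEDAI version, and SRI-5 to SRI-8 change only the SLEDAI cut-off (3.6.5).
- **(m)BICLA.** The fifth criterion in 3.4.3.6 (numbered 5 in 3.6.5) requires that no treatment failure has occurred. It names "new or increased immunosuppressives or anti-malarials", steroid increases outside the protocol allowance, and premature discontinuation of study treatment.
- **Rescue.** Sections 3.2.3.2 and 3.3.6.2 and the synopsis make a rescued subject a non-responder for the primary endpoint only. On staying on study drug, 3.2.3.2 says: "The Investigator will also assess if study drug administration can be continued or not, except in case of initiation of forbidden treatment".
- **After stopping study drug.** Such subjects "should return for the Early Termination Visit, planned within 3 weeks after the last study drug administration" (3.2.3.2; 3.4.1.3 agrees), and have a Follow-up Visit 12 weeks after the last dose. Section 3.1.1 separates the two kinds of follow-up: "Subjects will be followed for efficacy through Week 48, and for safety through Week 58".
- **Treatment-failure endpoint.** Section 3.6.5 has it "defined as non-protocol allowed increase in steroid dose, start i.v. or i.m. steroids, start or increase of immunosuppressant", with no mention of anti-malarials or discontinuation. The synopsis and 3.6.5.1 use the same shorter definition.

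**The concern.** mSRI and mBICLA are built from the same three instruments and will be read side by side at Week 24. Under the stated rules they differ in two ways: in what they measure, and in how they treat rescue and discontinuation. If they disagree, a reader cannot tell which difference is responsible.

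This matters more than for a minor endpoint. SRI is the first secondary endpoint named in 3.1.1, and mSRI is among the endpoints listed for exposure-response modelling in 3.6.7. The treatment-failure proportion is tabulated by arm, but it does not correct the (m)SRI rates. Its definition is also narrower than the one in (m)BICLA, so it cannot fully account for a gap between the two.

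**Working it through.** **Rescue.** Take a subject given a new immunosuppressant for a flare and kept on study drug.

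| | mBICLA | mSRI |
|---|---|---|
| Score criteria at Week 24 | may be met | may be met |
| Treatment-failure criterion | not met | none exists |
| Result | non-responder | responder, if the scores are met |

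The scores need not reveal the rescue. SLEDAI-2K looks back 30 days (Appendix 9.7): from Week 24 (day 168), to day 168 − 30 = 138. BILAG-2004 compares the last 4 weeks with the 4 before (Appendix 9.6), so it reaches back to day 168 − 56 = 112, or Week 16. A flare treated and settled before then can leave no trace.

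**Denominator.** Days run from baseline. Allow the last dose to be 7 days late (missed-visit rule, 3.4.1.2), Early Termination up to 21 days later, and visits ±5 days.

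| Last dose | Latest Early Termination | Target window opens |
|---|---|---|
| Week 18 | 126 + 7 + 21 = 154 | Week 24: 168 − 5 = 163 (not reached) |
| Week 20 | 140 + 7 + 21 = 168 | 163 (reachable) |
| Week 42 | 294 + 7 + 21 = 322 | Week 48: 336 − 5 = 331 (not reached) |
| Week 44 | 308 + 7 + 21 = 336 | 331 (reachable) |

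The 12-week Follow-up Visit can coincide with a target week (last dose at Week 12 gives Week 24; Week 36 gives Week 48). Whether BILAG and SLEDAI are scored there cannot be checked, because the schedule grid is not in the text.

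**Size, illustration only.** The protocol gives no SRI rate, so there is no figure of its own to reproduce. The mBICLA planning values in 3.6.3 are borrowed: 60 per arm, 25% v 50%, 15% discontinuation in each arm. That is 9 discontinued and 51 observed per arm.

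- If the rates apply to all mITT subjects: 15/60 = 25.0% v 30/60 = 50.0%, difference 25.0 points. Observed: 15/51 = 29.4% v 30/51 = 58.8%, difference 29.4 points.
- If they apply to subjects still on drug: counting discontinuation as non-response gives 0.85 × 25 = 21.3% v 0.85 × 50 = 42.5%, difference 21.3 points. Observed: 25.0% v 50.0%, difference 25.0 points.
- Either way, rates and difference are multiplied by 1/0.85 = 1.18, and the ratio stays 2.0.
- Equal discontinuation of 10% gives 15/54 v 30/54, difference 27.8 points; 20% gives 15/48 v 30/48, difference 31.3 points.

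**Imbalance, assumed values.** Keeping 25% v 50% on all mITT subjects, with discontinuation given as placebo/active:

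- 10%/20%: 0.50/0.80 − 0.25/0.90 = 62.5 − 27.8 = 34.7 points.
- 20%/10%: 0.50/0.90 − 0.25/0.80 = 55.6 − 31.3 = 24.3 points.
- 25%/5%: 0.50/0.95 − 0.25/0.75 = 52.6 − 33.3 = 19.3 points.

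Each rescued subject who meets the SRI criteria adds 1/51 = 2.0 points to that arm. Three in each arm give 18/51 = 35.3% v 33/51 = 64.7%, and the difference stays 29.4. With 20% rescued on placebo and 5% on active, of whom 30% to 50% meet the criteria:

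- Placebo: (15 + 3.6)/51 = 36.5% to (15 + 6)/51 = 41.2%.
- Active: (30 + 0.9)/51 = 60.6% to (30 + 1.5)/51 = 61.8%.
- Difference: 24.1 down to 20.6 points.

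**Steroid-reduction endpoints.** Medication is recorded up to the Follow-up Visit (3.3.6), which for an early stopper is 12 weeks after the last dose. Recording ends before Week 40 if the last dose is before about Week 28 (28 + 12 = 40), and before Week 48 if it is before about Week 36 (36 + 12 = 48).

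**The case against.** The strongest defence is that SRI is an established three-part index and that reporting scored status regardless of rescue is a legitimate descriptive summary. No test or stated decision rests on it: the model that may guide dose choice is fitted to mBICLA (3.6.5.1), and treatment failures are tabulated by arm. This stands as far as it goes. The index definition needs no change, and the point concerns the analysis rule only.

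The denominator part is also open to challenge. The protocol states no denominator. The ±5 days is a scheduling window, not an analysis window, and the 7-day late limit is not absolute, since for longer delays the site contacts the monitor. Mapping of Early Termination data is commonly SAP content. All of this stands, so this part is inference. It does not reach the rescue part: the protocol itself sets observed data for every secondary efficacy endpoint, and 3.6.5.1 refers only missing mBICLA response to the SAP.

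A reader might go further and infer that the observed-data rule favours the active arms. The documents do not support that, because they give no rescue or discontinuation imbalance, and the assumed cases above move the difference both ways. A reader might equally infer that every rescued subject can count as an mSRI responder. Forbidden treatment ends study drug, so those subjects would leave the denominator instead.

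Finally, recording of medication up to the Follow-up Visit might suggest that the steroid-reduction endpoints are safe. For early stoppers that visit comes too soon.

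**Conclusion.** The rescue part holds on the text alone: the same subject can be an mBICLA non-responder and an mSRI responder at one visit. The denominator part is the natural reading of observed data together with the visit plan, but the schedule grid and any SAP visit mapping could change it.

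The primary test and its error rate are unaffected. The harm is that Week 24 mSRI and mBICLA differ in handling rule as well as in construct. With borrowed mBICLA rates and equal 15% discontinuation, rates and difference rise by a factor of 1.18 (25.0 to 29.4 points). Any other net shift needs an imbalance that the protocol does not give, so neither its size nor its direction can be stated in advance.

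Separately, the treatment-failure definitions contradict each other. The criterion in (m)BICLA and the rescue text in 3.2.3.2, 3.3.6.2 and the synopsis include anti-malarials; the definitions in 3.6.5, 3.6.5.1 and the statistical part of the synopsis do not. This should be corrected, but it does not threaten the trial's main conclusion.

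**What to change.** In 3.6.5.2 and the synopsis:

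1. For SRI, mSRI, SRI-5 to SRI-8 and BILAG improvement, at each scheduled visit, count a subject as a non-responder if a treatment failure as described in the fifth criterion of 3.4.3.6, including premature discontinuation, has occurred by that visit (that is, if the criterion is **not** met), or if response data at that visit are missing.
2. Keep the observed-case tables as supportive.
3. State that the fifth criterion governs (m)BICLA over time, so that the observed-data wording does not conflict with it.
4. Reconcile the treatment-failure definition in the synopsis, 3.6.5 and 3.6.5.1 with the fifth criterion and with the rescue text on anti-malarials. Show discontinuation as its own row in the failure table.
5. State a rule for discontinued subjects in the steroid-reduction endpoints.

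The three-criterion definition in 3.4.3.7 stays as it is. The cost is wording and a few extra tables, with no new data collection. The downside is lower headline secondary response rates.

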Secondary endpoints will include:

- Composite endpoint (m)BICLA over time.
- Composite endpoint mSRI as well as standard SRI over time.
- (m)SRI with more stringent (m)SLEDAI-cut-offs: SRI-5, SRI-6, SRI-7, SRI-8 over time.
- Change from baseline in mSLEDAI-2K total score as well as standard SLEDAI-2K measured over time.
- Number and percent of subjects with BILAG-2004 improvement.
- BILAG-2004 (total score) over time.
- Improvement in individual organ systems of the BILAG-2004 over time.
- Number of BILAG-2004 systems in which activity increased, decreased or remained the same compared to previous visit (BILAG-2004 systems tally) over time.
- Change from baseline in PGA over time.
- Change from baseline in patient's global assessment over time.
- Change from baseline in proteinuria/urine sediment/serum creatinine/eGFR over time.
- Proportion of treatment failures (defined as non-protocol allowed increase in steroid dose, start i.v. or i.m. steroids, start or increase of immunosuppressant) at Week 24 and at Week 48.

- Reduction in flare rate at Week 24 and at Week 48.
 - Severe flare defined as a new A score in any system of the BILAG-2004 index; moderate flare defined as a new B score following a C, D or E score.
 - SLEDAI flare index (SFI).
- Percent change from baseline in daily dose of steroids at Week 24 and 48.
- Percent subjects whose prednisone equivalent dose was >7.5 mg/day at baseline and reduced to ≤7.5 mg/day during Weeks 40–48 without experiencing a flare.
- Percent subjects who are able to discontinue prednisone by Week 48 without experiencing a flare.
- Changes from baseline in the physical and mental component scores of SF-36 at Week 24 and at Week 48.
- 28 Joints count over time and change from baseline in 28 joint count over time.
- Cutaneous lupus erythematosus disease area and severity index (CLASI) over time and change from baseline evaluation at Week 12, 24 and Week 48.
- PK parameters.
- PD markers, including total sIL-6R, CRP, fibrinogen, anti-dsDNA, C3, C4, CH50.

Pharmacokinetics

Samples for determination of ALX-0061 serum levels.

Pharmacodynamics

Samples for determination of biomarker levels, including but not limited to total sIL-6R, CRP, fibrinogen, anti-dsDNA, C3, C4, CH50.

Samples for determination of additional biomarker levels (exploratory), including but not limited to uMCP-1, plasma cells, T helper 17 (Th17) and regulatory T (Treg) cells.

Immunogenicity

Samples for determination of anti-ALX-0061 antibodies.

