Safety

Safety assessments will include:

- Physical examination.
- Vital signs measurement.
- Electrocardiogram (ECG).
- Blood chemistry (including liver enzymes and lipids), hematology (including neutrophils and platelets) and coagulation parameters. Lupus anti-coagulant (LA), anti-cardiolipin (aCL) and anti-β₂-glycoprotein I (β₂-GPI) antibodies will be evaluated at screening and Week 24.

- Adverse events (AEs) (including local tolerability and hypersensitivity reactions) and serious AEs.

Statistical Methods:*Sample size and Power*

Up to approximately 300 subjects will be randomized over 5 treatment arms in a 1:1:1:1:1 ratio. Randomization will be stratified by geographic region.

Simulations were performed to evaluate the power of detecting a significant dose-response relationship, i.e., whether changes in ALX-0061 dose regimen lead to significant changes in mBICLA response rate at Week 24 by using the MCP-Mod methodology [1]. A set of 5 plausible candidate models containing both monotonous and non-monotonous exposure-response shapes was defined. For these models an estimated placebo response rate of 25%, and a difference in response rate between the ALX-0061 dose regimen with the largest response rate and placebo of 25% was assumed, taking into account a discontinuation rate of 15% (homogeneous over treatment arms). With this methodology a sample size of 60 subjects per arm will provide at least 85% power at a family-wise 5% significance level.

Primary efficacy endpoint evaluation:

mBICLA response rates at Week 24 will be analyzed using the MCP-Mod methodology. The analysis will be performed using the modified intent-to-treat (mITT) population of all subjects who have received at least 1 administration of study drug and according to the treatment for which they were assigned.

Subjects with missing mBICLA response data at Week 24, including those who have discontinued study drug before Week 24, as well as subjects with treatment failure, will be treated as non-responders (non-response imputation approach). Treatment failure is defined as non-protocol allowed increase in steroid dose, start i.v. or i.m. steroids, start or increase of immunosuppressant.

Primary efficacy endpoint evaluation will also be performed using the per-protocol (PP) population.

Summary statistics (frequencies, proportions) for mBICLA response rate at Week 24 and Week 48 will be provided by treatment group.

All other evaluations:

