3.6.5. EVALUATION OF EFFICACY PARAMETERS

The adjudication committee will also evaluate appropriateness of data for evaluating the primary endpoint.

The primary endpoint is the percentage of subjects who achieved a response at Week 24 according to the composite mBICLA (BILAG-based Combined Lupus Assessment) score. BICLA responders are defined as subjects who meet all of the following criteria:

- (1) BILAG-2004 improvement: all A scores at baseline improved to B/C/D, and all B scores improved to C or D.
- (2) no worsening in disease activity: no new BILAG-2004 A scores and ≤ 1 new B score.
- (3) no worsening of total mSLEDAI-2K score from baseline.
- (4) no significant deterioration ($< 10\%$ worsening) in PGA.
- (5) no treatment failure (i.e., new or increased immunosuppressives or anti-malarials; or non-protocol allowed increased oral or parenteral corticosteroids; or premature discontinuation from study treatment).

The following efficacy analyses will be performed in addition to the primary analysis:

- Composite endpoint (m)BICLA over time (through Week 48) will be summarized by treatment group.
- Composite endpoint mSRI as well as standard SRI over time (through Week 48) will be summarized by treatment group.
- (m)SRI with more stringent (m)SLEDAI-cut-offs: SRI-5, SRI-6, SRI-7, SRI-8 over time (through Week 48) will be summarized by treatment group.
- Change from baseline in mSLEDAI-2K total score as well as standard SLEDAI-2K measured over time (through Week 48) will be summarized by treatment group.
- Number and percent of subjects with BILAG-2004 improvement.
- BILAG-2004 (total score) over time (through Week 48) will be summarized by treatment group.
- Improvement in individual organ systems of the BILAG-2004 over time (through Week 48) will be summarized by treatment group.

- Number of BILAG-2004 systems in which activity increased, decreased or remained the same compared to previous visit (BILAG-2004 systems tally) over time (through Week 48) will be summarized by treatment group.
- Change from baseline in PGA over time (through Week 48) will be summarized by treatment group.
- Change from baseline in patient's global assessment over time (through Week 48) will be summarized by treatment group.
- Change from baseline in proteinuria/urine sediment/serum creatinine/eGFR over time (through Week 48) will be summarized by treatment group.

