3.6.5.1. PRIMARY EFFICACY ENDPOINT

mBICLA response rates at Week 24 will be analyzed using the MCP-Mod methodology [1]. The method entails a unified strategy to the analysis of data from dose-response studies which combines multiple comparison and modeling techniques. In general, the existence of several candidate parametric models is assumed and multiple comparison techniques are used to choose the model most likely to represent the true underlying dose-response curve,

while preserving the family-wise error rate. The selected model may further be used to guide the choice of adequate doses.

The analysis will be performed using the mITT population of all subjects who have received at least 1 administration of study drug and according to the treatment for which they were assigned.

Subjects with missing mBICLA response at Week 24, including those who have discontinued study drug before Week 24, as well as subjects with treatment failure, will be treated as non-responders (non-response imputation approach). Treatment failure is defined as non-protocol allowed increase in steroid dose, start i.v. or i.m. steroids, start or increase of immunosuppressant. Details on how missing mBICLA response is defined and handled will be provided in the SAP.

Primary efficacy endpoint evaluation will also be performed using the PP population.

Summary statistics (frequencies, proportions) for mBICLA response rate at Week 24 will be provided by treatment group.

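### (m)BICLA over time falls under the observed-data rule although the Week 24 primary analysis counts drop-outs and missing responses as failures, and the rule for Week 48 differs between synopsis and body

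*Protocol*

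**What the plan says.** - **Secondary endpoints.** The synopsis puts (m)BICLA over time first in its list of secondary endpoints. Section 3.6.5 lists it among the analyses additional to the primary one: "Composite endpoint (m)BICLA over time (through Week 48) will be summarized by treatment group". The series therefore includes Week 24 and Week 48.
- **Data rule for secondary endpoints.** Section 3.6.5.2: "All secondary efficacy endpoints will be summarized by treatment group, using the observed data in the mITT population". The synopsis repeats this under its heading for all other evaluations. Neither place makes an exception for responder composites.
- **Data rule for the primary endpoint.** Section 3.6.5.1 counts as non-responders "Subjects with missing mBICLA response at Week 24, including those who have discontinued study drug before Week 24, as well as subjects with treatment failure". It leaves further detail on missing mBICLA response to the SAP.
- **Endpoint definition.** Section 3.4.3.6 gives the general BICLA definition, not tied to a visit. Its last criterion, numbered (5) in section 3.6.5, lists among treatment failures "or premature discontinuation from study treatment".
- **Visits after stopping study drug.** Under section 3.4.1.3 such subjects "should return for an early termination visit within 3 weeks after the last study drug administration", and have one follow-up visit 12 weeks after the last dose. The section describes no continued efficacy visits.
- **Week 48.** Under primary efficacy endpoint evaluation, after the non-response rule, the synopsis says: "Summary statistics (frequencies, proportions) for mBICLA response rate at Week 24 and Week 48 will be provided by treatment group". The matching sentence in section 3.6.5.1 names Week 24 only.

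**The concern.** The endpoint contains its own rule for drop-outs: someone who stops study drug early is a failure. The observed-data rule pulls the other way, because a subject who has left the visit schedule has no BILAG, SLEDAI or PGA score at later visits. If that subject is dropped from the table, the response rate is computed on those who stayed, and a known failure disappears.

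Two things are at stake. First, Week 24 mBICLA appears both as the primary result and as one point of the time course, and the two values need not agree. Section 3.1.1 says BICLA responses are documented over time to allow assessment of time of onset; a curve that misses the primary Week 24 value serves that purpose poorly. Second, dropping discontinuers raises the reported rate most in the arm that loses most subjects.

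**Working it through.** **The plan's own figure.** The nearest stated figure is the power in section 3.6.3: at least 85% with 60 per arm and a family-wise 5% level. It cannot be reproduced exactly, because the five candidate shapes, the sidedness and the way the 15% discontinuation enters are not given. With two assumed sets of five shapes, one-sided 5%, and 25% against 50% with 60 per arm, the simulated minimum power over shapes is 0.88 to 0.89, in line with the statement. With 51 per arm the minimum is 0.82 to 0.84; with 21.25% against 42.5% and 60 per arm it is 0.79 to 0.81. This neither confirms nor refutes the stated power, and nothing below depends on it.

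**Inputs (section 3.6.3).** 60 subjects per arm; placebo response 25%; largest difference 25 points, so 50% in the best regimen; discontinuation d = 15%, the same in all arms. The protocol does not say whether 25% and 50% are rates in all subjects or in completers, so both are shown.

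**Formula.** If every discontinuer leaves the denominator, observed rate = non-response rate / (1 − d). Subjects observed per arm: 60 × 0.85 = 51.

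| Reading of 25% and 50% | Rule | Placebo | Best regimen | Difference (points) |
|---|---|---|---|---|
| All-subject rates | Non-response | 15/60 = 25.0% | 30/60 = 50.0% | 25.0 |
| All-subject rates | Observed data | 15/51 = 29.4% | 30/51 = 58.8% | 29.4 |
| Completer rates | Non-response | 0.25 × 0.85 = 21.25% | 0.50 × 0.85 = 42.5% | 21.25 |
| Completer rates | Observed data | 25.0% | 50.0% | 25.0 |

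On either reading the two rules differ at the same visit by a factor of 1/0.85 = 1.18.

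**Unequal discontinuation (assumption; the protocol plans equal rates).** Take two arms, both at 25% under the non-response rule.
- 10% against 20% discontinued: 0.25/0.90 = 27.8% and 0.25/0.80 = 31.3%, an apparent gain of 3.5 points from drop-out alone.
- 5% against 25% discontinued: 0.25/0.95 = 26.3% and 0.25/0.75 = 33.3%, a gain of 7.0 points.

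**Week 48 (assumed cumulative discontinuation of 15% to 30%).** A non-response rate of 25% becomes 0.25/0.85 = 29.4% to 0.25/0.70 = 35.7%. A rate of 50% becomes 58.8% to 71.4%.

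**If discontinuers are kept as failures.** Subjects still on treatment with a missing Week 24 score remain. They are non-responders in the primary summary and absent from the observed-data summary. The protocol gives no figure for them. As a scale, one such subject in an arm with 30 responders gives 30/60 = 50.0% in one table and 30/59 = 50.8% in the other.

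**The case against.** The strongest reply is that criterion (5) belongs to the definition and is not limited to Week 24. Stopping study drug is a recorded fact, so a discontinuer's non-response could itself be called observed. On that reading discontinuers stay in every denominator and sections 3.4.3.6, 3.6.5 and 3.6.5.2 agree. This reading is open, and the protocol does not choose. A reader might therefore infer too much in concluding that the whole time course contradicts the endpoint definition; the text supports only that discontinuers can leave the denominator. Even on the kinder reading, on-treatment subjects with a missing score are still handled differently in the two Week 24 summaries.

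A second reply is that section 3.6.5.1 leaves the definition and handling of missing mBICLA to the SAP, which was not available here. That sentence sits in the primary-endpoint section and does not lift the fixed rule in section 3.6.5.2.

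Third, the synopsis can be read as placing Week 48 under the primary rule. That is fair, and it means one cannot say that Week 48 is simply on observed data. Because section 3.6.5.1 names Week 24 only, the supportable point is an inconsistency.

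Finally, an observed-data table beside a non-response primary is not in itself an error. That stands, and the fix keeps one.

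**Conclusion.** The point holds as an unresolved conflict of rules in descriptive summaries. The protocol puts (m)BICLA over time on observed data without exception, makes discontinuation a failure within the same endpoint, and treats missing responses as failures only for the Week 24 primary analysis. For Week 48 the synopsis and body differ.

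Under the planning inputs, with every discontinuer dropped, the Week 24 difference between arms is 29.4 against 25.0 points if the planning rates are all-subject rates, or 25.0 against 21.25 if they are completer rates. If discontinuers are kept as observed failures, only on-treatment missing scores remain, and the protocol gives no basis for sizing them. The figures for unequal drop-out and for Week 48 rest on assumed discontinuation rates.

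Two further inferences are not supported. The primary result is not at risk: the MCP-Mod analysis has its own rule, and its alpha and power are unchanged. Nor does the protocol say that these curves will be used to judge durability; section 3.1.1 mentions time of onset, and early visits are where cumulative drop-out is smallest. The change is worth making because it is cheap and removes a second value for the primary endpoint.

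**What to change.** In section 3.6.5.2 and the matching synopsis paragraph, exempt (m)BICLA from the observed-data rule. Suggested wording:

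> At each visit through Week 48, (m)BICLA response is derived for every mITT subject. A subject with treatment failure or discontinuation of study drug up to that visit, or without an evaluable (m)BICLA response at it, counts as a non-responder, as for the primary endpoint. An observed-data summary is given as supportive.

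Then align the mBICLA summary sentence in section 3.6.5.1 with the one in the synopsis, so that both name the same visits under the same rule, and carry the wording into the SAP.

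The cost is one sentence in each place and one extra table. Reported rates at later visits will be slightly lower than on observed data.
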